4.6.3 Trial and Site Discontinuation

The Sponsor has the right to terminate this trial at any time. Reasons for terminating the trial may include, but are not limited to, the following:

- The incidence or severity of adverse events in this or other studies indicates a potential health hazard to patients
- Patient enrollment is unsatisfactory

The Sponsor will notify the investigator if the Sponsor decides to discontinue the trial.

The Sponsor has the right to close a site at any time. Reasons for closing a site may include, but are not limited to, the following:

- Excessively slow recruitment
- Poor protocol adherence
- Inaccurate or incomplete data recording
- Non-compliance with the International Conference on Harmonisation (ICH) guideline for Good Clinical Practice
- No trial activity (i.e., all patients have completed the trial and all obligations have been fulfilled)

5. ASSESSMENT OF SAFETY

5.1 SAFETY PLAN

Pirfenidone is approved for the treatment of IPF in the US, and for the treatment of mild to moderate IPF in the EEA and Canada ([Esbriet SmPC 2015](#); [Health Canada 2016](#); [US FDA 2015](#)). However, the efficacy and safety of pirfenidone in patients with unclassifiable ILD has not been fully elucidated. The safety plan for patients in this trial is based on clinical experience with pirfenidone in completed and ongoing studies predominately involving patients with IPF. The anticipated important safety risks for pirfenidone are outlined below. Please refer to the pirfenidone Investigator's Brochure for a complete summary of safety information.

Several measures will be taken to ensure the safety of patients participating in this trial. Eligibility criteria have been designed to exclude patients at higher risk for toxicities. Patients will undergo safety monitoring during the trial, including assessment of the nature, frequency, and severity of adverse events. In addition, guidelines for managing adverse events, including criteria for dosage modification and treatment interruption or discontinuation, are provided below.

An iDMC will review safety data and advise on trial conduct (see Section [3.1](#)). The procedures that will be used by the iDMC will be detailed in an iDMC charter.

5.1.1 Risks Associated with Pirfenidone

Treatment with pirfenidone was consistent with the known safety profile and generally well tolerated in patients who received treatment in the clinical development program.

Almost all patients experienced an adverse event (99.0% in the pirfenidone 2403 mg/day group and 97.9% in the placebo group). The most common adverse events in the pirfenidone group were GI events (nausea, diarrhea, dyspepsia, vomiting, gastroesophageal reflux disease [GERD], and constipation), respiratory-related events (cough, dyspnea, IPF, upper respiratory tract infection, nasopharyngitis, bronchitis, and sinusitis), fatigue, decreased weight, anorexia, back pain, arthralgia, headache, dizziness, insomnia, rash, and photosensitivity reactions.

5.1.1.1 Hepatic Function

Elevations in ALT and AST $>3 \times$ ULN have been reported in patients receiving therapy with pirfenidone. Rarely, these have been associated with concomitant elevations in bilirubin. LFTs (ALT, AST, and bilirubin) should be conducted prior to the initiation of treatment with pirfenidone and subsequently at monthly intervals for the first 6 months. In the event of significant elevation of liver aminotransferases, the dose of pirfenidone should be adjusted or treatment discontinued according to the guidelines listed in [Table 3](#). See Sections 5.4.2.11 and 6.4.1 of the Investigator's Brochure for more details.

Patients with clinically significant hepatic impairment will be excluded from this trial (see Section 4.1.2).

5.1.1.2 Gastrointestinal effects

Gastrointestinal events of nausea, diarrhea, dyspepsia, vomiting, GERD, and abdominal pain have been more frequently reported in the pirfenidone treatment groups than in the placebo groups. Dose reduction or interruption for gastrointestinal events was required in 18.5% of patients in the pirfenidone 2403 mg/day group compared with 5.8% of patients in the placebo group. In addition, 2.2% of patients in the pirfenidone 2403 mg/day group discontinued treatment due to a gastrointestinal event, as compared with 1.0% of patients in the placebo group. The most common (>2%) gastrointestinal events that led to dose reduction or interruption were nausea, diarrhea, vomiting, and dyspepsia. Dose modifications may be necessary in some cases of gastrointestinal adverse reactions. Taking pirfenidone with food is recommended. See Sections 5.4.2.10 and 6.4.1 of the Investigator's Brochure for more details.

The incidence of gastrointestinal events was higher early in the course of pirfenidone treatment (with the highest incidence occurring during the initial 3 months) and usually decreased over time.

5.1.1.3 Photosensitivity Reaction or Rash

Exposure to direct sunlight (including sunlamps) should be avoided or minimized during treatment with pirfenidone (see Investigator's Brochure for more details). Patients should be instructed to use an effective sunblock daily, to wear clothing that protects against sun exposure, and to avoid other medicinal products known to cause photosensitivity. Patients should be instructed to report any symptoms of photosensitivity reaction or rash. Dose adjustments or temporary treatment discontinuation may be necessary for photosensitivity reaction or rash. See Sections 5.4.2.13 and 6.4.1 of the Investigator's Brochure for more details.

5.1.1.4 Angioedema

Reports of angioedema (some serious), such as swelling of the face, lips, and/or tongue which may be associated with difficulty breathing or wheezing, have been received in association with use of pirfenidone in the post-marketing setting. Therefore, patients who develop signs or symptoms of angioedema following administration of pirfenidone should immediately discontinue treatment. Patients with angioedema should be managed according to standard of care. Pirfenidone should not be used in patients with a history of angioedema due to pirfenidone treatment. See Sections 5.4.2.16 and 6.4.1 of the Investigator's Brochure for more details.

5.1.1.5 Dizziness

In the pooled Phase 3 analysis (PIPF-004/006/016), dizziness was reported for a larger proportion of pirfenidone patients than placebo patients (18.0% pirfenidone vs. 11.4% placebo), and the majority of pirfenidone patients who reported dizziness first did so

during the initial 3 months of treatment (72/112, 64.3%). Two (0.3%) pirfenidone patients and one (0.2%) placebo patient had Grade 3 dizziness. There were no Grade 4 events, serious adverse events, hospitalizations, treatment discontinuations, or deaths for dizziness in either group. See Sections 5.4.2.9 and 6.4.1 of the Investigator's Brochure for more details.

An analysis of the relationship between dizziness and subsequent falls revealed that six of 112 (5.4%) pirfenidone patients who reported dizziness experienced a fall at some time after the first report of dizziness.

5.1.1.6 Fatigue

In the pooled Phase 3 analysis (PIPF-004/006/016), fatigue was reported for 26.0% of pirfenidone patients and 19.1% of placebo patients. The majority of pirfenidone patients who reported fatigue first did so during the initial 9 months of treatment (127/162, 78.4%), with 81/162 (50.0%), experiencing it within the first month. In the pirfenidone group, 1.1% of patients had a Grade 3 event; there were no Grade 4 events, serious adverse events, hospitalizations, treatment discontinuations, or deaths. In the placebo group, 0.8% of patients had a Grade 3 event, one (0.2%) patient had a serious adverse event, and one (0.2%) patient was hospitalized for fatigue; there were no Grade 4 events, deaths, or treatment discontinuations. See Section 6.4.1 of the Investigator's Brochure for more details.

5.1.1.7 Weight loss

In the pooled Phase 3 analysis (PIPF-004/006/016), the adverse event of weight decrease was reported for a larger proportion of pirfenidone patients than placebo patients (10.1% pirfenidone vs. 5.4% placebo), and the majority of pirfenidone patients who reported an adverse event of weight decrease first did so during the initial 6 months of treatment (39/63, 61.9%). In the pirfenidone group, two (0.3%) patients had Grade 3 adverse events, one (0.2%) patient had a serious adverse event, and five (0.8%) patients discontinued trial treatment for this adverse event; there were no Grade 4 events, hospitalizations, or deaths. In the placebo group, one (0.2%) patient had a serious adverse event and was hospitalized; there were no Grade 3 or 4 events, deaths, or treatment discontinuations for this adverse event. See Sections 5.4.2.14 and 6.4.1 of the Investigator's Brochure for more details.

5.1.1.8 Management of Increases in QT Interval

In the event of a QTcF interval of >500 ms or an increase from baseline of >60 ms, a repeat ECG must be obtained within 24 hours. If the QTcF finding is confirmed by the repeat ECG and verified by the site (trial center) or local cardiologist, pirfenidone treatment should be discontinued and a decision on trial treatment discontinuation should be made, as described in Section 4.6.1.. If an alternative explanation is identified (e.g., electrolyte abnormalities, co-medications known to prolong the QT interval, and

severe bradycardia) and the abnormality resolves, restarting trial treatment should be considered by the investigator in consultation with the Medical Monitor or designee. If the investigator, in consultation with the Medical Monitor or designee, considers it clinically appropriate to recommence trial treatment, treatment should be restarted as described in [Table 2](#) .

5.1.2 **Management of Patients Who Experience Specific Adverse Events**

Guidelines for management of specific adverse events are outlined in [Table 3](#) .

Table 3 Guidelines for Management of Patients Who Experience Specific Adverse Events with Pirfenidone

Event	Action to Be Taken
Elevated aminotransferase results	
 • For patients with a >3 to <5 × ULN increase in ALT or AST levels without hyperbilirubinemia: 
 • Discontinue confounding medications • Monitor the patient closely, including repeating liver chemistry tests • Maintain the full daily dose, if clinically appropriate, or reduce or interrupt the dose (e.g., until liver chemistry test results are within normal limits) with subsequent re-titration to full dose if well tolerated. • For patients with a >3 to <5 × ULN increase in ALT or AST levels with symptoms or hyperbilirubinemia: 
 • Discontinue pirfenidone and do not rechallenge the patient. • For patients with a >5 × ULN increase in ALT or AST levels: 
 • Trial treatment should be permanently discontinued.
Gastrointestinal disorders	
 • Dose modifications may be necessary in some cases of gastrointestinal adverse reactions. • Taking pirfenidone with food is recommended.
Photosensitivity reaction and rash	
 • Exposure to direct sunlight (including sunlamps) should be avoided or minimized during treatment with pirfenidone. • Instruct patients to: 
 • Wear clothing that protects against sun exposure • Avoid other medicinal products that cause photosensitivity • Report symptoms of photosensitivity reaction or rash. • Adjust dose or temporarily discontinue treatment (if necessary). • Use an effective sunblock on a daily basis.
Angioedema	
 • Immediately discontinue treatment. • Manage patients according to standard of care. • Pirfenidone should not be used in patients with a history of angioedema.

ALT=alanine aminotransferase; AST=aspartate aminotransferase; ULN=upper limit of normal

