4.6.2 Trial Treatment Discontinuation

Patients must discontinue trial treatment if they experience any of the following:

- Pregnancy
- Hepatic or renal impairment
- LFT elevations that require discontinuation
- Angioedema

The primary reason for early trial treatment discontinuation should be documented on the appropriate eCRF. Patients who discontinue trial treatment prematurely will not be replaced.

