5.2.3 Adverse Events of Special Interest (Immediately Reportable to the Sponsor)

Adverse events of special interest are required to be reported by the investigator to the Sponsor immediately (i.e., no more than 24 hours after learning of the event; see Section 5.4.2 for reporting instructions). Adverse events of special interest for this trial include the following:

- Cases of potential drug-induced liver injury that include an elevated ALT or AST in combination with either an elevated bilirubin or clinical jaundice, as defined by Hy's law (see Section 5.3.5.6)
- Suspected transmission of an infectious agent by the trial treatment, as defined below:

Any organism, virus, or infectious particle (e.g., prion protein transmitting transmissible spongiform encephalopathy), pathogenic or non-pathogenic, is considered an infectious agent. A transmission of an infectious agent may be suspected from clinical symptoms or laboratory findings that indicate an infection in a patient exposed to a medicinal product. This term applies only when a contamination of the trial treatment is suspected.

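### Table 3's first aminotransferase bullet does not exclude symptoms, so a symptomatic patient with normal bilirubin meets both a may-continue rule and a stop-without-rechallenge rule

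*Protocol*

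**What the plan says.** The aminotransferase entry of Table 3 (Protocol Section 5.1.2) has three bullets.

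- **First bullet.** ALT or AST above 3 and below 5 × ULN, an "increase in ALT or AST levels without hyperbilirubinemia". The site stops confounding medications, monitors closely and repeats the liver tests. On dosing it says "Maintain the full daily dose, if clinically appropriate, or reduce or interrupt the dose", with re-titration to full dose allowed if tolerated.
- **Second bullet.** The same band, an "increase in ALT or AST levels with symptoms or hyperbilirubinemia". The instruction is "Discontinue pirfenidone and do not rechallenge the patient".
- **Third bullet.** ALT or AST above 5 × ULN: permanent discontinuation, whatever the symptoms or bilirubin.

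Two other sections bear on the choice. Section 5.1.1.1 says that after a significant rise "the dose of pirfenidone should be adjusted or treatment discontinued according to the guidelines listed in" Table 3. Section 4.6.2 includes "LFT elevations that require discontinuation" among the events after which trial treatment must stop, without saying which elevations those are.

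The table also reaches open-label treatment: Section 4.3.4 ties open-label dosing to Section 4.3.2.1, which points to Section 5.1.1 for dose modification.

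**The concern.** The two bullets for the 3 to 5 × ULN band look like complements but are not. The second is triggered by either of two findings; the first is closed by only one of them. A patient with symptoms and normal bilirubin therefore satisfies both entry conditions, and the actions cannot both be followed: one allows full dose or a return to it, the other forbids rechallenge.

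What is at stake is the safety of an individual patient. A site that reads the first bullet literally could keep dosing, or re-titrate, someone whom the table means to take off drug for good.

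**Working it through.** The plan states no figure on this point, so there is nothing to reproduce. The check is to apply the bullets literally to every combination and then to look for a rule that settles any overlap.

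**Step 1. Apply both bullets within the band (above 3, below 5 × ULN).**

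| Symptoms | Raised bilirubin | First bullet | Second bullet | Result |
|---|---|---|---|---|
| No | No | applies | – | investigator's discretion |
| No | Yes | – | applies | stop, no rechallenge |
| Yes | Yes | – | applies | stop, no rechallenge |
| Yes | No | applies | applies | conflicting instructions |

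The overlap is 1 of 4 combinations.

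**Step 2. Ask which bullet was meant to win.** Suppose the symptom trigger were deleted from the second bullet. It would then cover the two raised-bilirubin combinations only. The single combination whose membership changes is symptoms with normal bilirubin. The symptom trigger therefore does its work for exactly this patient, and if the first bullet governed, it would do nothing. The second bullet is also a flat instruction, while the first is conditional on clinical judgement. The intent is recoverable.

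**Step 3. Look for a stated precedence rule.**

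- Section 5.1.1.1 refers back to Table 3.
- Section 4.6.2 makes the stop mandatory but does not define the elevations. It adds force once the second bullet is taken to apply; it does not itself say that the second bullet applies.
- Section 5.3.5.6 is a reporting rule for Hy's law cases and needs bilirubin above 2 × ULN or jaundice.
- The SAP has no dosing rule on this point.

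None says that the second bullet prevails.

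**Step 4. Test the upper boundary.** At 4.9 × ULN the first or second bullet applies; at 5.1 × ULN the third applies; at exactly 5 × ULN no bullet applies, because the band ends below 5 and the third bullet starts above it.

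**Step 5. Repeat Step 1 with symptoms excluded from the first bullet.** No symptoms and normal bilirubin goes to the first bullet; the other three combinations go to the second. The overlap falls from 1 of 4 to 0 of 4, and every combination has exactly one action.

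**The case against.** The strongest reply is that an ordinary reading already resolves the conflict. The second bullet is the only text that mentions symptoms, so it is the specific rule. Section 5.1.1.1 sends the reader to Table 3, the second bullet there requires discontinuation, and Section 4.6.2 then makes that stop mandatory over a discretionary alternative. This largely stands, and it is why the point is minor. It remains an inference that each site has to draw for itself.

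A second reply is that Section 5.1.1.1 cites the Investigator's Brochure for liver details, and the Brochure may settle the matter. It is not among the documents reviewed, so the point concerns the protocol wording only.

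A third is that the SAP (Section 4.5.8) dates the primary analysis to March 2019, after the double-blind period. An amendment could no longer change double-blind dosing. That limits the practical benefit but does not make the wording right.

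A fourth is that Table 3 does not define symptoms. Nausea is among the most common events under pirfenidone (Section 5.1.1), and fatigue was reported in 26.0% of pirfenidone patients in the pooled Phase 3 analysis (Section 5.1.1.6). Which symptoms should force a permanent stop is a harder question, and the wording change alone does not answer it. This stands as a limit of the fix.

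A reader might also infer that the sponsor would not hear of such a patient, because the liver event of special interest requires "an elevated ALT or AST in combination with either an elevated bilirubin or clinical jaundice". The documents do not support going that far. A laboratory abnormality with symptoms must be recorded as an adverse event (Section 5.3.5.4), and the investigator may class it as a significant medical event, which brings the 24-hour report (Section 5.2.2).

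**Conclusion.** The first bullet is wrong as written, and the error is minor. It creates conflicting instructions for one identifiable patient type, those with ALT or AST above 3 and below 5 × ULN, symptoms and normal bilirubin. The intended answer, to stop without rechallenge, can be inferred but is not stated. The conclusion rests on a literal reading of Table 3 and on the absence of a precedence rule in the protocol and SAP. Type I error, power and the primary analysis are unaffected.

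Two stronger readings are tempting. Section 5.1.1.1 says of elevations above 3 × ULN: "Rarely, these have been associated with concomitant elevations in bilirubin". A reader might infer that symptoms are therefore the more usual way into the second bullet. The sentence concerns bilirubin only, and the documents do not say how often symptoms accompany these elevations. A reader might also infer that some number of patients were kept on drug wrongly. The documents give neither the frequency of the affected combination nor any instance of a site following the first bullet against the second, so no count can be given.

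**What to change.** Change the scope of the first bullet to: *>3 to <5 × ULN without symptoms or hyperbilirubinemia*. Symptomatic patients then fall only under the second bullet.

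Assign exactly 5 × ULN to one band. Starting the third bullet at *≥5 × ULN* is the cautious choice; the documents do not dictate it, and extending the lower band to include 5 would also close the gap.

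The cost is two lines of one table in a protocol amendment, with no new procedures. The downside is possibly a few more permanent discontinuations among symptomatic patients whom some sites would have managed under the first bullet.

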5.2 SAFETY PARAMETERS AND DEFINITIONS

Safety assessments will consist of monitoring and recording adverse events, including serious adverse events and adverse events of special interest, performing protocol-specified safety laboratory assessments, measuring protocol-specified vital signs, and conducting other protocol-specified tests that are deemed critical to the safety evaluation of the trial.

Certain types of events require immediate reporting to the Sponsor, as outlined in Section 5.4.

5.2.1 Adverse Events

According to the ICH guideline for Good Clinical Practice, an adverse event is any untoward medical occurrence in a clinical investigation patient administered a pharmaceutical product, regardless of causal attribution. An adverse event can therefore be any of the following:

- Any unfavorable and unintended sign (including an abnormal laboratory finding), symptom, or disease temporally associated with the use of a medicinal product, whether or not considered related to the medicinal product
- Any new disease or exacerbation of an existing disease (a worsening in the character, frequency, or severity of a known condition), except as described in Section 5.3.5.9
- Recurrence of an intermittent medical condition (e.g., headache) not present at baseline
- Any deterioration in a laboratory value or other clinical test (e.g., ECG, X-ray) that is associated with symptoms or leads to a change in trial treatment or concomitant treatment or discontinuation from trial treatment
- Adverse events that are related to a protocol-mandated intervention, including those that occur prior to assignment of trial treatment (e.g., screening invasive procedures such as biopsies)

5.2.2 Serious Adverse Events (Immediately Reportable to the Sponsor)

A serious adverse event is any adverse event that meets any of the following criteria:

- Is fatal (i.e., the adverse event actually causes or leads to death)
- Is life threatening (i.e., the adverse event, in the view of the investigator, places the patient at immediate risk of death)
 - This does not include any adverse event that had it occurred in a more severe form or was allowed to continue might have caused death.
- Requires or prolongs inpatient hospitalization (see Section 5.3.5.10)
- Results in persistent or significant disability/incapacity (i.e., the adverse event results in substantial disruption of the patient's ability to conduct normal life functions)

- Is a congenital anomaly/birth defect in a neonate/infant born to a mother exposed to trial treatment
- Is a significant medical event according to the investigator's judgment (e.g., may jeopardize the patient or may require medical/surgical intervention to prevent one of the outcomes listed above)

The terms "severe" and "serious" are not synonymous. Severity refers to the intensity of an adverse event (e.g., rated as mild, moderate, or severe, or according to National Cancer Institute Common Terminology Criteria for Adverse Events [NCI CTCAE]; see Section 5.3.3); the event itself may be of relatively minor medical significance (such as severe headache without any further findings).

Severity and seriousness need to be independently assessed for each adverse event recorded on the eCRF.

Serious adverse events are required to be reported by the investigator to the Sponsor immediately (i.e., no more than 24 hours after learning of the event; see Section 5.4.2 for reporting instructions).

